11.2 Analyses

All analyses will be done using R (the R Foundation for Statistical Computing) or Stata (version 14, Stata Corporation) in Lesotho. For all tests, we will use 2-sided p-values with alpha 0.05 level of significance. A detailed data analysis plan will be developed separately.

Clusters will be set as unit of randomization (stratified by district), whereas individuals are set as unit of analysis. Multilevel random effects models will be used to analyze the data. We will present a CONSORT flowchart of the participants, including screening, enrollment and follow-up. The following analysis sets will be used in this trial:

1. Intention-to-treat (ITT) set: All study participants will be evaluated according to cluster assignment at randomization
2. Per-protocol (PP) set: This set includes all participants who completed the study without a major protocol deviation

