5.1 Primary endpoint

In care with documented viral suppression at 12 months, defined as the proportion of participants in care with a documented VL <20 copies/mL 12 months (range: 9 – 15 months) after enrolment out of all participants enrolled

- i. *Rational for VL suppression level at 20 copies/mL: VL determination will be done on COBAS TaqMan® HIV-1 Test, v2.0 (Roche Diagnostics) using plasma, and has a reliable lower limit of detection of 20 copies/mL*
- ii. *Definition of "in care": at least one ART visit in the defined window*
 - I. *Including participants who transferred out to any other health facility with known outcome (documented proof of follow-up visit or laboratory test)*
 - II. *Excluding participants who died (all-cause), were lost to follow-up (LT FU), or were known defaulters/refusers, i.e. were more than 2 months late for ART refill with a reason available (e.g. currently no money for clinic-visit, busy working in South Africa, etc.)*
- iii. *The study will use VL results from routine VL monitoring. To synchronize routine VL monitoring and study VL monitoring, study staff will help ensure each site has the capacity to collect these samples and will support existing systems that help to provide results back to sites. VLs will only be performed on individuals who return for visits and no tracking will be performed by the study staff to obtain VLs.*

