11.2.1 Primary analysis

The primary analysis will use multi-level logistic regression models (on the intention-to-treat set) including clinic as random effect to assess the difference between viral suppression rate in the intervention versus control arm, adjusted for the pre-specified randomization stratification factor, baseline VL, and relevant

baseline factors that may be randomly unbalanced between intervention and control clusters. All results will be presented as odds ratios and their respective 95% confidence intervals (CI).

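### The per-protocol set requires study completion, so on its ordinary reading it drops the deaths, losses and defaulters that the primary endpoint counts as failures

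*Combined protocol and SAP*

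**What the plan says.** Section 11.2 introduces two sets with the words "The following analysis sets will be used in this trial". For ITT it says: "All study participants will be evaluated according to cluster assignment at randomization". For PP it says: "This set includes all participants who completed the study without a major protocol deviation". Neither completion nor a major deviation is defined, and a detailed analysis plan is deferred to a separate document.

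Section 11.2.1 assigns the main result to ITT: "The primary analysis will use multi-level logistic regression models (on the intention-to-treat set) including clinic as random effect". Section 11.2.2, which covers secondary, exploratory, subgroup and sensitivity analyses, does not mention the PP set.

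The primary endpoint in section 5.1 is a proportion measured 12 months "after enrolment out of all participants enrolled". Success requires being in care with a documented viral load below 20 copies/mL. The definition of being in care carries the condition "Excluding participants who died (all-cause), were lost to follow-up (LT FU), or were known defaulters/refusers". These people therefore stay in the denominator and count as failures. The same section adds: "VLs will only be performed on individuals who return for visits and no tracking will be performed by the study staff to obtain VLs".

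**The concern.** Retention is half of the endpoint and a main target of the intervention. Section 2.1 describes this age group as prone to leaving care, and section 4.3.5 describes an app that tracks refills and keeps the peer educator in regular contact with the participant. If the model works partly by keeping people in care, a set restricted to completers conditions on part of the effect. The two arms of that set are then no longer comparable by randomisation.

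What is at stake is any PP estimate that is reported. A PP difference smaller or larger than the ITT difference could arise from the definition of the set alone, and a reader could take it as evidence about the robustness of the main result. If the set were also applied to the secondary endpoints, 12-month mortality and loss to follow-up would be close to zero, and engagement in care close to 100%, by construction.

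**Working it through.** **Planning figures (section 11.1).** Inputs: control rate 70%, a 20% increase, 15 participants per clinic, 10 clinics per arm, ICC 0.05, two-sided alpha 0.05.

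- Design effect: 1 + (15 − 1) × 0.05 = 1.70, as stated.
- Reading the increase as absolute (70% vs 90%), 90% power needs 82 per arm. 82 × 1.7 = 139.4, and 139.4 / 15 = 9.3, rounded up to 10 clinics per arm, which gives 300 participants.
- Power at 150 / 1.7 = 88.2 effective per arm is 92.0% by the normal approximation and 90.0% with a t reference on 18 df. The stated 90% is reproduced.
- Reading the increase as relative (70% vs 84%) gives only 60.0%, so 70% vs 90% is used below.

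**Failures at the planning rates.** Control: 150 × 0.30 = 45. Intervention: 150 × 0.10 = 15.

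**What a completers-only set does.** Assume that every non-completer is a failure, as section 5.1 implies for deaths, losses and defaulters. With non-completion c (control) and i (intervention), the rates among completers are 0.70 / (1 − c) and 0.90 / (1 − i). The documents give neither c nor i, so both are assumptions.

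Worked case, c = 20% and i = 5%:
- Control: 150 × 0.20 = 30 leave, all failures (30 of 45, or 67%). 105 / 120 = 87.5%.
- Intervention: 150 × 0.05 = 7.5 leave, half of the 15 failures. 135 / 142.5 = 94.7%.
- The difference falls from 20 to 7.2 points. The crude odds ratio falls from (0.90/0.10) / (0.70/0.30) = 3.86 to (135/7.5) / (105/15) = 2.57.

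Range, with the all-enrolled rates fixed at 70% vs 90%:

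| Control non-completion | Intervention non-completion | Completers, control vs intervention | Difference (points) |
|---|---|---|---|
| 0% | 10% | 70.0% vs 100.0% | +30.0 |
| 0% | 0% | 70.0% vs 90.0% | +20.0 |
| 10% | 5% | 77.8% vs 94.7% | +17.0 |
| 15% | 5% | 82.4% vs 94.7% | +12.4 |
| 20% | 5% | 87.5% vs 94.7% | +7.2 |
| 25% | 5% | 93.3% vs 94.7% | +1.4 |
| 30% | 5% | 100.0% vs 94.7% | −5.3 |
| 30% | 0% | 100.0% vs 90.0% | −10.0 |

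The outer rows are limits, not expectations: at 30% in control, or 10% in intervention, every failure in that arm is attrition.

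**A pure retention effect.** Suppose 80% of completers are suppressed in both arms and completion is 90% (intervention) vs 80% (control), again assumed. All enrolled: 0.90 × 0.80 = 72% vs 0.80 × 0.80 = 64%, a difference of 8 points. Completers: 80% vs 80%, a difference of 0. The zero follows from assuming equal suppression among completers.

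**The case against.** The strongest reply is that nothing reported depends on this set. The primary analysis is ITT, the trial tests superiority, no named analysis uses PP, and the detailed plan is deferred. That stands: a reader might infer that the primary result or the power is biased, or that the plan offers PP as a check on ITT, and the documents support neither. The retention effect is not lost from the trial either. Sections 5.2 and 11.2.2 cover engagement in care, loss to follow-up, mortality and attrition separately. But section 11.2 does say that the set will be used and fixes its rule, and a later plan would inherit that rule unless it is corrected.

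The second reply is that completion is undefined. Section 14.1 treats withdrawal from the study separately from the care outcomes in section 5, and section 12.1 takes follow-up data from routine records. A participant who defaulted or died could have a known 12-month outcome and be called a completer. This reading is possible, and on it the problem disappears for those participants. The text does not adopt it, though, and leaving the term open allows membership to be settled after outcomes are known.

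Third, a reader might infer that the set removes all the failures that the endpoint counts. It does not: those in care with a viral load of 20 copies/mL or more remain.

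Finally, the sizes rest on assumed attrition. That is correct, and it is why a range is shown. Attenuation, inflation and reversal are all possible, and none is predicted.

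**Conclusion.** The point holds as a defect in a stated definition, limited to PP estimates. On the ordinary reading of completion, the PP set conditions on a post-randomisation outcome that is also a component of the endpoint. At the planning rates, the completers-only difference is 7.2 points instead of 20 under assumed non-completion of 20% vs 5%. It runs from −10 to +30 points over control 0–30% and intervention 0–10%. These figures assume that the all-enrolled rates equal the planning rates, that every non-completer is a failure, and that no one else is excluded for a major deviation. They are crude proportions and do not come from the planned mixed model. The correction is worth making before outcome data are seen, but the main conclusion of the trial does not depend on it.

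**What to change.** Change the PP definition in section 11.2, and carry it into the separate analysis plan, as follows:

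- Remove the completion condition.
- Exclude only for major deviations listed in advance and judged without knowledge of the outcome, for example a participant found to have been ineligible at enrolment.
- Keep deaths, losses to follow-up and defaulters in the set as failures, exactly as in the ITT analysis.
- Name the analyses that use the set, and label PP as supportive only.
- State whether returning to facility-based care, which section 12.3 allows for participants in the PEBRA model, counts as a deviation. If it does, it removes people from the intervention arm only.

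Do not make clinic-level delivery of the model a PP criterion without an agreed threshold. Delivery is itself post-randomisation, section 4.3.5 makes it subject to feasibility, and the exclusions would fall mainly on intervention clinics, of which there are only 10.

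The cost is a short change of wording and an agreed list of deviations. No new data are needed, and sample size and conduct do not change. The downside is that the PP set will differ little from ITT and so will add little information.

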11.2.1 Primary analysis

The primary analysis will use multi-level logistic regression models (on the intention-to-treat set) including clinic as random effect to assess the difference between viral suppression rate in the intervention versus control arm, adjusted for the pre-specified randomization stratification factor, baseline VL, and relevant

baseline factors that may be randomly unbalanced between intervention and control clusters. All results will be presented as odds ratios and their respective 95% confidence intervals (CI).

11.2.2 Baseline characteristics; secondary, exploratory, subgroup and sensitivity analyses

Baseline characteristics will be presented according to randomized groups, no formal testing will be performed. Categorical variables will be described as absolute and relative frequencies and continuous variables as medians and interquartile ranges. As with the primary analysis, secondary (binary and categorical) endpoints will primarily be analyzed with multi-level logistic regression models and presented as odds ratios and their respective 95% CI. To estimate incidence of attrition (defaulting from care), a poisson regression will be used. We will do a quadrature check of the model fit and if found to be unreliable, we will utilize generalized estimating equations. The effect of sociodemographic and clinical determinants (age groups, gender, employment status, WHO-stage, CD4-count, HIV/ART history, HIV/AIDS knowledge, HIV/AIDS stigma) on key study outcomes will be assessed by including interaction terms in the model. If the interaction term is found to be significant, effect estimates will be summarized descriptively by subgroup. As the study is not powered for these pre-planned subgroup analyses, these results will be considered exploratory.

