4.3.4 Procedures in all study clusters

A trained PE per cluster will actively screen all AYPLHIV for eligibility. If eligible, the PE will continue with the baseline assessment, using a tablet-based application. The following data will be collected (from medical records and patient interview):

- Consent documentation (and if not consenting, then reason for refusal and stop data collection)
 - Details about consent process see in section 13.1
- ART number
- Clinic/Cluster
- Year of birth
- Gender
- Village
- Cellphone number
- Date of ART initiation
- WHO-stage at ART initiation
- Laboratory information: CD4 at ART initiation, last CD4, VL history and baseline VL*
- Co-morbidities
- TB history
- Co-medication
- ART regimen history
- Socio-demographic data including age, gender, level of education, employment status, marital status, pregnancy
- Structural data incl. distance and time and costs (incl. opportunity costs) to visit the health facility
- HIV/AIDS knowledge and stigma¹⁹
- Adherence: Pill count and setting- & age-validated treatment adherence questions²⁰⁻²²
- Quality of Life (QoL): WHO HIV QoL questionnaire (whoqol_hiv_bref questionnaire)²³⁻²⁵
- Quality of Care (QoC): a setting-validated perceived QoC & patient satisfaction questionnaire²⁶

*Note: Baseline VL is defined as the last VL within the previous 12 months, taken from the medical records (bukana, patient file, laboratory databases). If no VL within previous 12 months available, then the participant will be sent to the nurse for blood draw for routine VL measurement. This is not a study-specific procedure, but standard of care. If the patient is new in care and due for 6 months VL, then the 6m routine VL will be taken as baseline VL.

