5.2 Secondary endpoints

- a) Adherence to ART at 3 months (range 2.5 – 3.5), 6 months (range 5 – 8) and 12 months (range 9 – 15) after enrolment
 - i. *Assessed by 4 different setting- and age-validated ART adherence questions²⁰⁻²²:*
 - a. *pill count: change in percentage*
 - b. *"When was the last time you missed any medications?" [i) past week, ii) 1-2 weeks ago, iii) 3-4 weeks ago, iv) never]: Dichotomous outcome missed doses vs. no missed doses in the past month*
 - c. *"ART missed at two or more consecutive days within last month?" ("drug holiday" question)*
 - d. *"How would you rate your adherence over the last month" [i) very poor, ii) poor, iii) fair, iv) good, v) very good, vi) excellent]: Dichotomous outcome adherent vs non-adherent (anything less than 'excellent')*
- b) Quality of Life (QoL) at 6 months (range 5 – 8) and 12 months (range 9 – 15) after enrolment
 - i. *Assessed by WHO QoL in PLHIV: WHO HIV QoL questionnaire (whoqol_hiv_bref questionnaire with 31 five-point Likert Scale items with categorical outcome)²³⁻²⁵*
- c) Perceived quality of ART Care (QoC) / patient service satisfaction at 6 months (range 5 – 8) and 12 months (range 9 – 15) after enrolment
 - i. *Assessed by a setting-validated QoC and patient service satisfaction questionnaire (12 five-point Likert Scale items with categorical outcome)²⁶ by an external data collector, not the PE*

- d) Engagement in care at 6 months, defined as the proportion of participants engaged in care 6 months (range 5 – 8) after enrolment out of all participants enrolled
 - i. *Definition of “in care”: at least one ART visit in the defined window*
 - I. *Including participants who transferred out to any other health facility with known outcome (documented proof of follow-up visit or laboratory test)*
 - II. *Excluding participants who died (all-cause), were lost to follow-up (LTFU), or were known defaulters/refusers, i.e. were more than 2 months late for ART refill with a reason available (e.g. currently no money for clinic-visit, busy working in South Africa, etc.)*
- e) Alternative viral suppression at 12 months, defined as the proportion of participants with a documented VL <1000 copies/mL 12 months (range 9 – 15) after enrolment out of all participants enrolled
 - i. *Rational for alternative VL suppression definition at 1000 copies/mL: According to the currently used Lesotho national guidelines, an unsuppressed VL is defined as a 1000 copies/mL or more*

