11 SAMPLE SIZE AND ANALYSIS PLAN

11.1 Sample size calculation

Based on data from our database with VL results from all health facilities of Butha-Buthe and Mokhotlong district (VL platform, www.1stowards909090.org/db), there are on average 15 AYPLHIV per health center with an overall viral suppression rate of 70%, thus, we expect this proportion of viral suppression for the control clusters. An overall target sample size of 300 AYPLHIV in 20 clusters (10 per arm) will provide us 90% power (design effect of 1.7) to detect a 20% increase of viral suppression in the intervention group, assuming a type 1 error of 0.05, and an intra-cluster correlation coefficient (ICC) of 0.05, an ICC based on similar studies^{28,29}.

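### The quality-of-life and quality-of-care questionnaires go to logistic models with no scoring rule, pill-count change has no named model, and none of the three has its own baseline as a pre-specified covariate

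*Combined protocol and SAP*

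**What the plan says.** Section 11.2.2 states that "secondary (binary and categorical) endpoints will primarily be analyzed with multi-level logistic regression models and presented as odds ratios", with 95% confidence intervals. The only other models there are a Poisson regression for attrition and generalized estimating equations as a fallback if the quadrature check fails. Section 11.2.1 also says that all results will be odds ratios.

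Section 5.2 describes the QoL endpoint as the "whoqol_hiv_bref questionnaire with 31 five-point Likert Scale items with categorical outcome". It describes QoC in the same way, with 12 five-point items. Neither has a total score, a domain score, a cut-point, or a choice between binary, ordinal and multinomial logistic regression. Two of the adherence questions in the same section are explicitly made dichotomous, with the split stated. The pill-count measure is given only as "pill count: change in percentage".

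Section 4.3.4 lists the baseline data for all clusters. These include "Quality of Life (QoL): WHO HIV QoL questionnaire (whoqol_hiv_bref questionnaire", the QoC questionnaire and pill count. The covariates in Section 11.2.1 are district, baseline viral load, and baseline factors that turn out to be unbalanced. Section 11.2.2 models the secondary analysis on the primary one and names no further covariate.

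**The concern.** A single odds ratio cannot be computed from 31 or 12 items until someone decides how to combine them and which logistic model to fit. The trial is open-label, so a scoring rule or cut-point chosen late is open to selective choice. Even a good choice within the logistic family uses less of the data than a linear model of the score.

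The plan also collects the best available predictor of each follow-up score, the same measure at enrolment, and does not commit to using it. As written, that value could enter only if it looked unbalanced, which makes the model depend on the data. With 20 clusters the trial has little precision to spare, and QoL and QoC are its main patient-reported results.

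**Working it through.** **The plan's own figure.** The plan gives a power calculation only for the primary endpoint: "An overall target sample size of 300 AYPLHIV in 20 clusters (10 per arm) will provide us 90% power (design effect of 1.7" with "on average 15 AYPLHIV per health center with an overall viral suppression rate of 70" percent, sized "to detect a 20% increase of viral suppression in the intervention group" (read as 70% versus 90%), intra-cluster correlation 0.05. On testing: "For all tests, we will use 2-sided p-values with alpha 0.05 level of significance".

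- Design effect = 1 + (15 − 1) × 0.05 = 1.70.
- Two proportions, 0.70 versus 0.90, 90% power: 82 per arm. 82 × 1.7 = 139.4, and 139.4 / 15 = 9.29, rounded up to 10 clusters per arm, or 300 in total.
- Effective size per arm = 150 / 1.7 = 88.2. Power is 92.0% by the normal approximation and 90.0% by a non-central t with 20 − 2 = 18 df and unpooled variance.

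The figure reproduces. No figure is given for QoL, QoC or pill count, so the rest uses stated assumptions.

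**Step 1: cost of the scale, relative to a linear model of a normally distributed score.**

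- *Split in two at proportion p.* Efficiency = φ(z_p)² / [p(1 − p)].
- *Five ordered categories, proportional odds.* Efficiency = (Σ r_i d_i)² / Var(r), where r_i is the mid-rank of category i and d_i is the normal density at its lower bound minus that at its upper bound.

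| Analysis | Efficiency | Loss |
|---|---|---|
| Five categories, 20% each | 0.888 | 11% |
| Five categories, 5/10/20/40/25% | 0.870 | 13% |
| Five categories, 3/7/15/35/40% | 0.823 | 18% |
| Split 50/50 | 0.637 | 36% |
| Split 70/30 | 0.576 | 42% |
| Split 80/20 | 0.490 | 51% |
| Split 90/10 | 0.342 | 66% |

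**Step 2: cost of leaving out the own baseline.** With baseline-to-follow-up correlation r, adjustment multiplies the variance by 1 − r². The share forgone is r²: 9%, 25% and 49% for r = 0.3, 0.5 and 0.7. It applies to what remains after step 1, so the combined loss is 1 − efficiency × (1 − r²):

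| | r = 0.3 | r = 0.5 | r = 0.7 |
|---|---|---|---|
| Five equal categories | 19% | 33% | 55% |
| Median split | 42% | 52% | 68% |

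**Step 3: what this means for power.** Take a standardised difference of 0.4, 150 per arm, design effect 1.7 and 18 df. Variance = 2 × 1.7 × (1 − r²) / (150 × efficiency). For the linear model without baseline, the standard error is √(3.4 / 150) = 0.1506 and the non-centrality is 0.4 / 0.1506 = 2.66.

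| Analysis | Power |
|---|---|
| Median split, no baseline | 52% |
| Five ordered categories, no baseline | 62-66% |
| Linear, no baseline | 71% |
| Linear with baseline, r = 0.3 | 75% |
| Linear with baseline, r = 0.5 | 83% |
| Linear with baseline, r = 0.6 | 88% |

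**The case against.** The strongest reply is that the plan never says QoL or QoC will be split in two. Section 5.2 reserves the dichotomous label for two adherence questions and uses a different word for the questionnaires, and Section 11.2.2 likewise separates binary from categorical endpoints. An ordinal logistic model needs no cut-point. Applied to a many-valued score, it would lose only about 4.5%. This stands. A reader might infer that the plan throws away a third to more than half of the information. The documents do not support that as a fact: it needs either a two-way split or an ordinal analysis combined with a baseline correlation of about 0.5 or more, and they state neither.

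A reader might also infer that pill count is sent to a logistic model. It is not. The logistic sentence is limited to binary and categorical endpoints, and the general statement in Section 11.2 that multilevel random effects models will be used could cover a linear mixed model. The gap is that no specific model is named. What the change is measured from is also undefined, so it may already use the baseline value.

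Nor is baseline adjustment ruled out for these endpoints. The covariate list in Section 11.2.1 can be read as carrying over, and an unbalanced baseline score could enter that way. So the own baseline is omitted, not excluded.

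Last, Section 11.2 announces a separate detailed analysis plan, which is not among the documents and would be a normal place for scoring rules and covariates. That lowers the stakes but does not remove the point. Section 11.2.2 already fixes the model class and the effect measure for categorical endpoints, and a later plan would have to depart from it to do better.

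**Conclusion.** The concern holds in a limited form. QoL and QoC are assigned to multilevel logistic models with odds ratios, without a scoring rule or model type. Pill-count change has no specific model. The own baseline, collected for all three, is not pre-specified as a covariate. A linear mixed model of the score with its own baseline is more precise and costs almost nothing.

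The size depends on choices that the plan leaves open: about 11-18% of the information if five ordered categories are used, 36-66% if the score is dichotomised between 50/50 and 90/10, and a further r² of what remains for the missing baseline. The illustrative power runs from 52% to 88%. These figures assume a normally distributed score, a standardised difference of 0.4, a full 150 per arm at follow-up, and a design effect of 1.7, which the plan states only for viral suppression. They also assume r between 0.3 and 0.6, and that baseline reduces between-clinic and within-clinic variance equally. None of these is given in the documents for these outcomes.

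These are secondary endpoints. The primary analysis and the sample size are unaffected. The change should be made before outcome data are seen.

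**What to change.** In Section 11.2.2:

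- Name the scoring rule for QoL domain scores and for the QoC score, using each instrument's own rule.
- Analyse these scores and the pill-count percentage with a linear mixed model that has clinic as random effect, and district and the same measure's baseline value as fixed covariates. Report adjusted mean differences with 95% confidence intervals.
- Define the pill-count measure, including what any change is measured from.
- Keep logistic models for endpoints that are binary by nature or by stated definition. Add the own baseline value as a covariate in the models for the dichotomous adherence items.
- Amend the statement in Section 11.2.1 that all results are odds ratios so that it allows mean differences for these endpoints.

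The cost is a few sentences and no new data. The small downside is that the score endpoints are no longer on the odds-ratio scale used elsewhere.

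### Subgroup estimates are promised only on condition of a significant interaction, so the subgroup contrasts shown will be exaggerated on average and consistency across the other factors may not be visible

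*Combined protocol and SAP*

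**What the plan says.** Section 11.2.2 of the combined protocol and SAP names eight determinants for subgroup work: "age groups, gender, employment status, WHO-stage, CD4-count, HIV/ART history, HIV/AIDS knowledge, HIV/AIDS stigma". Their effect "on key study outcomes will be assessed by including interaction terms in the model". The key outcomes are not listed, and no cut-points are given for the age groups, CD4 count or the knowledge and stigma scores.

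The display rule follows: "If the interaction term is found to be significant, effect estimates will be summarized descriptively by subgroup". The section then qualifies it: "As the study is not powered for these pre-planned subgroup analyses, these results will be considered exploratory".

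The significance level comes from section 11.2: "For all tests, we will use 2-sided p-values with alpha 0.05 level of significance". No separate level or multiplicity rule is given for interaction tests. The same section adds: "A detailed data analysis plan will be developed separately". That separate plan is not among the documents.

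No sentence says what is reported for a determinant whose interaction is not significant.

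**The concern.** The rule lets a p-value decide which subgroup results are laid out, in a setting where the plan concedes low power. When power is low, an interaction estimate reaches significance only if it is large, so the contrasts that get displayed are on average larger than the truth. A non-significant interaction in an unpowered test says little about whether the effect is consistent, yet the rule attaches no commitment to show it.

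What is at stake is interpretation. Section 2.3 justifies the model by the heterogeneous needs of this population, and section 3.4 lists scalability among the further objectives. Readers considering wider use will want to see how the effect varies by age, gender and disease stage. Under the written rule they may see an occasional exaggerated contrast and no estimates for the other factors.

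**Working it through.** **Inputs from the plan.** 300 participants, 20 clusters, 10 per arm, 15 per cluster, ICC 0.05, 70% suppression in control, a 20% increase, 90% power (section 11.1); two-sided 0.05 (section 11.2); eight determinants (section 11.2.2).

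**Assumptions, not in the plan.** Independent tests; one test per determinant; a binary factor split 50/50, giving 75 per cell; one or two key outcomes; a true ratio of odds ratios (ROR) of 1.5; normal theory on the log scale; a design effect on the interaction between 1 and the plan's full 1.7.

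**Step 1: the plan's own figure.**
- Design effect: 1 + (15 − 1) × 0.05 = 1.70, as stated.
- Reading the increase as absolute (70% to 90%): n per arm = [1.96 × √(2 × 0.8 × 0.2) + 1.28 × √(0.21 + 0.09)]² / 0.2² ≈ 82.
- 82 × 1.7 = 139.4 per arm, or 9.3 clusters of 15, rounded up to 10. That gives 150 per arm and 300 in total.
- Power at 150/1.7 = 88.2 effective per arm is about 92% (about 89% with continuity correction), consistent with the stated 90%.
- A relative reading (70% to 84%) gives only about 60%, so 70% versus 90% is used below.

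**Step 2: chance of a display when no interaction exists.**
- Eight tests (one outcome): 1 − 0.95⁸ = 0.337, or 34%.
- Sixteen tests (two outcomes): 1 − 0.95¹⁶ = 0.560, or 56%.
- Expected number displayed per outcome: 8 × 0.05 = 0.4 of 8.

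**Step 3: how large an interaction must look to be displayed.**
- SE of the log ROR, no design effect: √[2/(75 × 0.21) + 2/(75 × 0.09)] = 0.65. Threshold: exp(1.96 × 0.6506) = 3.6, or its inverse.
- With the full 1.7: 0.6506 × √1.7 = 0.848. Threshold: exp(1.96 × 0.848) = 5.3, or its inverse.
- With the rates held fixed, an unequal split raises the SE, so 50/50 is the favourable case.

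**Step 4: what is displayed when the true ROR is 1.5** (simulated normal estimates, keeping those with two-sided p < 0.05).

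| | No design effect | Design effect 1.7 |
|---|---|---|
| Probability of display | 9.6% | 7.7% |
| Geometric mean displayed ROR, ignoring direction | 4.8 | 7.6 |
| Geometric mean displayed ROR, signed | 4.1 | 5.2 |
| Displayed in the wrong direction | 5% | 10% |

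**Step 5: what this does to the two subgroup odds ratios.**
- The overall OR for 70% versus 90% is (0.9/0.1)/(0.7/0.3) = 3.86.
- Splitting a true ROR of 1.5 evenly around it gives subgroup ORs of 3.86 × √1.5 = 4.7 and 3.86/√1.5 = 3.1.
- With equal subgroups, selection acts on the difference and moves each log OR by half the excess. With no design effect the factor is √(4.14/1.5) = 1.66.
- The higher subgroup averages 4.72 × 1.66 = 7.8 when displayed, and the lower averages 3.15/1.66 = 1.9. The first is overstated and the second understated.

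**The case against.** Four points on the other side carry weight.

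First, the plan does not say that non-significant results are withheld. A reader might infer that they will never be seen, but the text is silent rather than prohibitive. Section 11.2.1 says that all results are given as odds ratios with 95% CIs, and the synopsis says much the same. That sentence sits under the primary analysis, so its reach is arguable. On one fair reading every interaction estimate is reported and only the by-subgroup breakdown is conditional. What stands is that no sentence commits to the fuller display.

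Second, display format is normal content for the separate analysis plan, which could change the rule. That is fair, but the protocol sentence is what that plan would inherit.

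Third, a reader might infer that every subgroup effect reported will be inflated, or that most of those shown will be chance findings. Neither is supported. Step 5 shows that the contrast is exaggerated while the lower subgroup effect is understated. The share of chance findings depends on how many true interactions exist, which the documents do not give. If none exist, nothing is displayed for a given outcome about 66% of the time (100 − 34).

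Fourth, the safeguards are real. The factors are named in advance, an interaction test is used rather than separate tests within subgroups, and the results are labelled descriptive and exploratory. These limit how strongly a finding can be claimed. They do not remove the selection or supply the missing estimates.

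**Conclusion.** The point holds as a weakness in reporting. Section 11.2.2 makes the by-subgroup display conditional on p < 0.05 for eight determinants in an analysis that the plan calls unpowered, and it makes no commitment for the rest. Contrasts that pass are exaggerated on average, and consistency across the other factors cannot be judged from what is promised.

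The size rests on the assumptions listed in the working. The thresholds of 3.6 to 5.3, and the displayed average of 4.8 to 7.6 against a true 1.5 (4.1 to 5.2 signed), are illustrations across the design-effect range, not predictions. Positively correlated tests would lower the 34% and 56%; more outcomes would raise them.

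The sample size, the error level and the primary analysis are untouched. This is a cheap improvement rather than a threat to the trial's conclusion.

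**What to change.** Replace the conditional sentence in section 11.2.2, and carry the change into the separate analysis plan. For every pre-specified determinant, report the subgroup estimates and the interaction estimate, each with a 95% CI, whatever the p-value. State the number of interaction tests, and keep the exploratory label. To make that number countable, name the key study outcomes and the cut-points for each determinant before the data are analysed.

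The cost is one extra table or figure, such as a forest plot, per key outcome. With no true interaction, all eight factors per outcome would then be visible instead of an expected 0.4, and the mean absolute z of the interactions shown would be about 0.80 rather than the 2.34 seen among those that pass the filter.
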